Measures. As detailed in Table 1 on the next page (and in “Inventory of Assessments” document attached), sleep quality indicators are primary outcomes; we will examine treatment mediators on outcomes. All outcomes are assessed at each time point. We will utilize objective and subjective measures because the latter capture aspects of sleep more salient to patients.^{131,132}

(1) Wrist actigraphy, a valid, objective method of estimating sleep-wake parameters.^{133,134} [will be assessed for two weeks at each time point. Actigraph data will be used to assess total sleep time and fragmentations.]

(2) The Consensus Sleep Diary (CSD)²² is a 9-item diary developed through expert and patient collaboration. Diaries, reliable ways to assess sleep,^{22,135,136} will be electronically accessed using any electronic device via Qualtrics, a secure online research data collection platform; to increase adherence, participants will receive daily text reminders with the link to the diary via REDCap.

(3) Additional validated measures are as detailed in Table 1 (and in attached “Inventory of Assessments” document). We will also collect process evaluation data (see attached “Group Implementation Checklist” and “Individual Implementation Checklist”).

Statistical Analysis. Statistical analysis in the context of an R21 must balance two primary agendas: (1)

effect size estimation and (2) tests of statistical significance. Our primary goal is to examine design feasibility, which will allow us to be poised for a subsequent full-scale IRGT. We plan to use information about potential design problems to guide modifications of design elements for a larger scale follow-up study, if warranted. Descriptive data analysis will proceed with formal hypothesis testing and model building in order to understand the distribution of the data and to check for outliers. We will examine patterns of missing data, paying special attention to the balance of missing data in study arms, and will impute missing data using multiple imputation approach.¹³⁷ We will examine univariate and joint distributions of potential confounders outcome variables; discrepancies will be corrected. Psychometric properties of outcome variables will be examined. We will transform continuous outcome variables if needed. Analyses will use the Intent-to-Treat (ITT) principle,¹³⁸ which requires subjects' data to be analyzed as randomized.

Table 1. Summary of Measures Assessing Outcomes

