Baseline	Sleep actigraphy (2 weeks)	During intervention (7 weeks)	Post-intervention	Sleep actigraphy (2 weeks)	Follow-Up (2.5 months post intervention)	Sleep actigraphy (2 weeks)	Measure	Construct	# of items	During...	Time duration	Notes
X							Participant demographics	Age, gender, grade, school, race, ethnicity	6	N/A	5 mins	
X							General Sleep Inventory (GSI)	Sleep location	10	Current	<5min	In baseline survey
	X		X		X		Actigraphy	Sleep duration, sleep onset latency, sleep efficiency				Participants wear actigraph for 2 weeks, return actigraph for data download and charging
	X			X		X	Core Consensus Sleep Diary (CSD)	Sleep duration; sleep fragmentation; subjective sleep quality	9	Daily	2-5 mins	
		X					National Youth Physical Activity Survey (NYPANS)	Daily physical activity (total Q8; vigorous Q10) in previous day	2	Daily	1 min	Control group only
X			X		X		Pittsburgh Sleep Quality Index (PSQI)	Sleep duration; sleep fragmentation	18	Last month	~5-15min	Omitted Q10
X			X		X		Adolescent Sleep Hygiene Scale (ASHS)	Sleep hygiene	33	Last month	~5min	
X			X		X		Perceived Stress Scale (PSS-14)	Stress	14	Last month	<5min	
X			X		X		PROMIS Ped Psychological Stress Experiences 8a	Stress	8	Last 7 days	<5min	
X			X		X		PROMIS Ped Anxiety 8a	Anxiety	8	Last 7 days	<5min	
X			X		X		PROMIS Ped Sleep 8a	Sleep-related impairment	8	Last 7 days	<5min	
X			X		X		MAAS-A	Mindfulness	14	Last 7 days	<5min	
			X				Participant Experience Survey – Part 1	Contamination, satisfaction, self efficacy				
			X		X		Participant Experience Survey – Part 2	Use of skills in last week				Treatment group only

3. Study Procedures

PHASE 1 – Development Phase

To develop *Sleeping Healthy/Living Healthy*, the PIs will use a 4-step iterative process.

Step 1: Identify Salient Intervention Components. We will initially identify salient intervention components four ways.

(1) The investigative team will update our literature review and review published sleep hygiene interventions to ensure we have the most relevant potential intervention components.

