Randomization. We will enroll 60 adolescents from two SBHCs in NYC (n=30 per SBHC). Within each school, we will randomize participants in equal numbers to the treatment (n=30) or control (n=30) group using urn randomization techniques¹³⁹⁻¹⁴¹. Participants will be randomized within each SBHC (2 arms x 2 SBHCs x 2 cohorts) in equal numbers to receive either the intervention or an attention control condition. Randomization of each participant will occur when the participant completes the baseline assessments. The urn randomization algorithm will be implemented using SAS 9.3 (SAS institute, 2002) by our biostatistician. This procedure conceals allocation to treatment or control from participants and study staff until just before the intervention begins. Sex and sleep duration at baseline will factor into the urn randomization procedure, making it more likely that groups will be balanced on these variables.

We will minimize contamination [using procedures used in our prior trials]: (1) train half the providers in each SBHC to deliver the intervention, allowing control participants to be seen by the other providers; (2) encourage control providers to not address sleep above and beyond what they would normally do when seeing non-intervention patients; [(3) ask treatment providers to not share the intervention content or materials with colleagues]; and (4) emphasize to the adolescents the importance of minimizing discussion of intervention content beyond the intervention setting.

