Implementation. *Sleeping Healthy/Living Healthy* (treatment) and *Sleep for Teens* (control) will run concurrently in two waves: one wave during the fall semester and a second wave in the spring semester. Both *Sleeping Healthy/Living Healthy* and *Sleep for Teens* will consist of five group sessions and two individual sessions delivered once a week over the course of seven weeks (see Table 2 below and “Sample Sleeping Healthy/Living Healthy Group Manual” attached). Sessions will be delivered in person at the SBHC or school, or remotely via Zoom. Each group will consist of 7-8 adolescent participants. *Sleeping Healthy/Living Healthy* will be implemented by two SBHC staff per group, with the same staff conducting individual sessions to build facilitator-participant rapport. *Sleep for Teens* will be run by non-SBHC staff. All group and individual sessions will be audio recorded using a secure Zoom account or a password-protected device to monitor fidelity. Recordings will be transmitted to authorized study personnel via encrypted message, and will be destroyed once fidelity checklists are completed.

Table 2. Treatment and Control Pilot Implementation

				FALL		FALL		SPRING		SPRING	
		Wave>		Wave 1A		Wave 1B		Wave 2A		Wave 2B	
		School>		GW	GW	IS 52	IS 52	GW	GW	IS 52	IS 52
		Implementer>		SBHC staff	Non-SBHC staff	SBHC staff	Non-SBHC staff	SBHC staff	Non-SBHC staff	TBD	Non-SBHC staff
		Arm>		Treatment	Control	Treatment	Control	Treatment	Control	Treatment	Control
Week		Duration	Intervention Topics	Control Topics							
1	Group 1	40m	Sleep basics, mindful breathing	Importance of sleep for health	1 group						
2	Group 2	40m	Good sleep practices, acupressure	Stress management	1 group						
3	1:1	20m	Review of sleep data & use of techniques, problem solve	Review of stress management techniques	7-8 meetings						
4	Group 3	40m	Sleep routines, tapping	Nutrition & physical activity	1 group						
5	1:1	20m	Review/problem solve, teach body awareness	Review of nutrition and physical activity	7-8 meetings						
6	Group 4	40m	Sleep environment & mindful attention	Time management	1 group						
7	Group 5	40m	Wrap up & celebration	Wrap up & celebration	1 group						

Notes: 8 x 7.5 participants = N of 60

Control topics: didactic content on importance of healthy sleep, stress management, nutrition, exercise, time management

Control sessions will be held at SBHC locations but will not be conducted by SBHC staff or providers

Compensation.

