1. Participants will be informed that the group and individual sessions will be audio recorded. For in-person sessions, their voices will be recorded, but no other likenesses will be recorded. Names and likenesses (pictures or live video) will not be recorded. For sessions delivered via Zoom, both audio and video will be

recorded due to Zoom's recording settings. However, the video file will be immediately destroyed, and only the audio file will be used for fidelity monitoring purposes.

2. The audio recordings will be stored temporarily on an encrypted and password protected computer.
3. The audio recordings will be used by only two individuals: the facilitator and a trained study staff member, both of whom will be responsible for completing the fidelity checklists. As soon as the fidelity checklists are completed, the audio recordings will be destroyed.
4. There will be no future use of the recordings once the fidelity checklists are completed.

Participants will be consented individually in a private Zoom appointment or phone call prior to the focus group or program start date, and all of these points will be reviewed.

9. Privacy Protections

We will ensure confidentiality is protected by taking several steps. Per CUIMC Institutional Review Board (IRB) guidelines, all members of the study staff must complete trainings in human subjects protection and HIPAA requirements, as well as ongoing training by the PIs and the Co-Investigators in all aspects of human subjects protection. The platforms we will use for data collection, Zoom and REDCap, will use only the CUIMC-hosted versions, which are HIPAA compliant. For purposes of the research database, each participant will be assigned a unique identifier that bears no systematic relation to the family, or school, or SBHC records. Information to be excluded from the research data base includes names of study participants, addresses, telephone numbers, school, clinician, and other information that has the potential to identify individuals. All outcome data will be de-identified by HIPAA standards using the "safe-harbor" method (i.e., all 18 PII elements will be stripped) prior to being stored on a password-protected, encrypted server.

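### Phase 2 treats 60 adolescents in eight groups and plans effect sizes and significance tests, but names no outcome model or group term and provides for no masked site or group code in the analysis file

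*Combined protocol and SAP*

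**What the plan says.** **Design.** Section 3 (Phase 2, Randomization) states: "Participants will be randomized within each SBHC (2 arms x 2 SBHCs x 2 cohorts) in equal numbers". Section 3 (Implementation) says that the two programmes "will run concurrently in two waves: one wave during the fall semester and a second wave in the spring semester", and adds: "Each group will consist of 7-8 adolescent participants". Table 2 shows one treatment and one control group per school in each semester, and its note multiplies 8 by 7.5 to reach 60. I take the two cohorts to be the two waves; the protocol does not say so in words. Five of the seven sessions are group sessions.

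**Analysis.** The Phase 2 Statistical Analysis in Section 2 names two agendas, "effect size estimation and (2) tests of statistical significance", and puts design feasibility first. It covers distribution checks, multiple imputation, psychometrics, transformation and intention to treat. It names no outcome model and no term for group, school or wave. The methods paper on this type of design (reference 112) is cited at the end of Section 1 in connection with the future full-scale trial. No section says which of its approaches is adopted.

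**Analysis file.** Table 1 collects "Age, gender, grade, school, race, ethnicity" at baseline. Section 9 then excludes from the research database "school, clinician, and other information that has the potential to identify individuals", and gives each participant a "unique identifier that bears no systematic relation to the family, or school, or SBHC records". Section 8 keeps files linking ID codes to names. No section mentions a coded site, wave or group variable.

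**Facilitators.** The Implementation text has two SBHC staff per treatment group and non-SBHC staff for control. Table 2 lists the implementer of one treatment group (Wave 2B, IS 52) as still to be determined. The paragraph on training and fidelity plans measures to limit differences between interventionists.

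**The concern.** Adolescents who share a group share facilitators, sessions and peers, so their outcomes may be correlated. Each group lies wholly within one arm, so this correlation adds to the variance of the arm comparison. An analysis without a group term does not count that variance: its tests reject too often and its intervals are too narrow. Hypothesis 2 compares arms on the primary sleep outcomes, and Section 2 says that Phase 2 is to supply effect sizes for the larger trial, so both uses are exposed.

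The privacy text bears on the same point. In Table 2 a group is exactly one combination of arm, school and wave. If Section 9 is followed as written and no code is added, the research database holds no variable that identifies the eight groups.

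**Working it through.** **1. The plan's own figure.** 2 arms x 2 SBHCs x 2 cohorts = 8 groups; 8 x 7.5 = 60. This reproduces the note to Table 2. The plan gives no alpha, power, SD or ICC to reproduce.

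**2. Assumptions.** ICC 0.01 to 0.10; two-sided 5% test; total variance 1; correlation of the outcome with its baseline value r = 0.5, acting at individual level; no dropout. None of these stands in the documents.

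**3. False rejection if groups are ignored.** The design effect is DE = 1 + (7.5 - 1) x ICC. A t-test on 58 df then rejects with probability of about 2 x P(T58 > 2.002/√DE). At ICC 0.05: DE = 1.325, 2.002/1.151 = 1.739, giving 8.7%. Simulation used eight groups of 7 or 8 with no arm effect, 40,000 trials per setting.

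| ICC | DE | Formula | Simulated t-test, 58 df | Simulated ANCOVA with school, wave and baseline, no group, 55 df |
|---|---|---|---|---|
| 0.01 | 1.065 | 5.7% | 5.8% | 6.0% |
| 0.02 | 1.13 | 6.5% | 6.6% | 7.0% |
| 0.05 | 1.325 | 8.7% | 8.8% | 10.2% |
| 0.10 | 1.65 | 12.5% | 12.9% | 16.0% |

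Covariates without a group term do not cure the problem. Baseline removes within-group variance, so the group component becomes a larger share of what is left.

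**4. False rejection on group means.** Baseline-adjusted group means reject 4.9-5.1% on 4 df (school and wave fitted) and 4.8-5.3% on 6 df (8 groups - 2 arms).

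**5. Precision.** Without baseline, the 95% half-width is t x √(4/60 x DE). If groups are ignored this is 2.002 x √(4/60) = 0.52 SD. On 6 df it is 0.67 / 0.73 / 0.81 SD at ICC 0.02 / 0.05 / 0.10. With baseline adjustment it is t x √(4/60 x (0.75 + 6.5 x ICC)), where 0.75 = 1 - 0.5².

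| ICC | 6 df (t = 2.447): formula; simulated | 4 df (t = 2.776): formula; simulated | School, wave and baseline, no group |
|---|---|---|---|
| 0.02 | 0.59; 0.60 | 0.67; 0.68 | 0.45 |
| 0.05 | 0.66; 0.66 | 0.74; 0.75 | 0.44 |
| 0.10 | 0.75; 0.75 | 0.85; 0.85 | 0.44 |

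Part of the widening is loss of df only. At ICC 0 the formula gives 2.447 x √0.05 = 0.55 SD on 6 df and 2.776 x √0.05 = 0.62 SD on 4 df (simulated 0.63), against 0.45 SD without group.

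**6. School alone.** With school explaining an assumed 5% of variance and ICC 0, the t-test that omits school rejects 4.5%, and unadjusted group means on 6 df reject 2.1%. Both are conservative, because allocation is balanced within school.

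**7. What eight groups can say about the ICC.** With 6 and 52 df, an estimate of 0.05 has a 95% interval of -0.07 to 0.44.

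**8. Shared facilitators.** With an assumed group ICC of 0.02 and facilitator variance of 0.03, the 4-df analysis rejects 7.5% if teams are shared across waves, and 8.1-9.9% with one control team.

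**The case against.** The strongest reply is that this is a feasibility pilot. The Statistical Analysis puts feasibility first, and Section 1 leaves powered efficacy testing to a later trial. At ICCs of 0.01 to 0.02 the excess is one or two percentage points. That is right, and it limits the weight of the point. It does not remove it, since significance tests and effect sizes are still planned.

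Three stronger readings are tempting, and the documents support none of them.

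- A reader might infer that the trial will analyse participants as independent. The plan nowhere says so; it leaves the model open.
- A reader might infer that Section 9 rules out a clustered analysis, or contradicts Table 1. Collecting school and later removing it is a sequence, not a contradiction. A masked code is not forbidden, linkage files exist, and the biostatistician runs the urn within each SBHC and so must know site at allocation. The attached inventory and checklists are not visible to us and may say more.
- A reader might infer that the effect sizes would be biased. With near-equal groups the point estimate is essentially unaffected; only its stated uncertainty and the p-values change.

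On facilitators, the plan has common training, bi-weekly supervision and a fidelity trigger at 85%. These may reduce facilitator variance, but they do not replace an analysis that allows for it. Finally, fitting school and wave uses two of six df, so the 4-df model is one valid choice and not the only one.

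**Conclusion.** The point holds as an omission that should be put right before the analysis file is built. The trial names itself an individually randomized group treatment trial and plans inference, but it specifies neither a model that judges arm against between-group variation nor the variables that such a model needs. If groups were ignored, the nominal 5% test would reject about 6% to 13% of the time over ICCs of 0.01 to 0.10, or about 6% to 16% with school, wave and baseline fitted but no group. The nominal half-width would be about 0.45 SD, where a valid analysis gives about 0.60 to 0.75 SD on 6 df or 0.68 to 0.85 SD on 4 df at ICCs of 0.02 to 0.10. These sizes rest on the assumed ICCs and r = 0.5, on reading cohorts as waves, and on facilitators not being shared across groups. They describe what would follow from an analysis that the plan leaves possible but does not state. The feasibility aims are untouched.

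**What to change.** 1. Amend Section 9 so that a restricted analysis file keeps coded, non-identifying variables for site, wave and treatment group (1-8).
2. For each Hypothesis 2 outcome, name the time point (post-intervention or 2.5 months) and test arm on group means adjusted for the outcome's baseline value, using the pooled within-group slope. Choose in advance between 6 df (arm only) and 4 df (arm, school and wave). The first is narrower; the second avoids a conservative test if schools differ.
3. Carry group into the imputation model, and pool with the matching complete-data df (6 or 4).
4. Report the ICC with its interval, and say that eight groups estimate it poorly.
5. Report the facilitator roster by group, reconcile the undetermined implementer in Table 2 with the text on SBHC staff, and state that the 5% level assumes facilitators are not shared across groups.

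The cost is an amendment to Section 9, a paragraph in the Statistical Analysis and three coded variables, with no extra participants or visits. The downsides are wider intervals, fewer df, and access control for coded cells of 7-8 minors, given the commitment in Section 8 against deductive disclosure. Shared facilitators would remain a limitation that this analysis cannot remove.

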Intervention Training and Fidelity. Providers at each SBHC will deliver the *Sleeping Healthy/Living Healthy* because we are creating a dissemination model leveraging existing resources. Drs. [name] and [name] have each trained providers to deliver interventions.¹⁴²⁻¹⁴⁶ To ensure consistency in training across SBHCs, we will use identical training procedures for each SBHC using a structured training curriculum [adapted from our prior research]. We will employ established procedures to minimize interventionist effect. Drs. [name] and [name] will provide training and lead bi-weekly supervision meetings. Group intervention and control sessions will be audio recorded; a trained study staff member will review each tape and complete a Fidelity Checklist based on Borrelli’s framework.¹²⁶ Because recording the individual sessions has the potential to interfere with provider-participant rapport, to assess fidelity of these sessions, immediately after each individual session, each provider will complete a Fidelity Checklist. For all Fidelity Checklists, a fidelity score is generated by dividing the number of covered elements by the total number of session elements; fidelity scores below 85% will trigger discussion in supervision meetings. [Fidelity Checklists will be examined for contamination, retraining providers as needed.]

Data Collection. Blinded trained study staff will interview adolescents three times: (1) baseline; (2) immediate post-intervention; and (3) 2.5-month follow-up. Interviews will take place at school or via telephone/Zoom during the school day; telephone interviews and/or online surveys will be utilized as needed to capture chronically absent students. Adolescents will wear the actigraphs for two weeks prior to each interview with actigraphy data being downloaded during the interview. The formative process evaluation includes immediate post-intervention interviews with the adolescents and SBHC providers and staff to obtain feedback regarding intervention procedures.

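### Does a treatment-only survey at both post-randomisation assessments undo the interviewers' blinding?

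*Combined protocol and SAP*

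**What the plan says.** The Data Collection paragraph of section 3 (Phase 2) states that "Blinded trained study staff will interview adolescents three times: (1) baseline; (2) immediate post-intervention; and (3) 2.5-month follow-up". It places these interviews at school or by telephone or Zoom, and adds that "telephone interviews and/or online surveys will be utilized as needed to capture chronically absent students". A separate sentence says that "The formative process evaluation includes immediate post-intervention interviews with the adolescents and SBHC providers and staff to obtain feedback regarding intervention procedures".

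Table 1 in section 2 lists the "Participant Experience Survey – Part 2", with the construct "Use of skills in last week" and a note limiting it to the treatment arm. Its two marks fall under Post-intervention and Follow-Up. Part 1 of the same survey is marked at post-intervention only and carries no such limit.

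On concealment, the Randomization paragraph of section 3 says: "This procedure conceals allocation to treatment or control from participants and study staff until just before the intervention begins". On session recordings, the Phase 2 list in section 8 says: "The audio recordings will be used by only two individuals: the facilitator and a trained study staff member", so that they can complete the fidelity checklists.

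Sections 2 and 7 refer to an attached Inventory of Assessments for the full list of instruments. That attachment is not part of the text under review.

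**The concern.** A form given in one arm only reveals the arm to whoever hands it over, before any answer is read. This form is due at every assessment after randomisation, and the protocol calls the interviewers at those assessments blinded. It does not say who gives the form, whether it comes before or after the outcome scales, or how interviewers stay unaware of the arm once sessions begin; the concealment sentence stops at that point. The feedback interviews and the review of recordings are two further routes by which staff could learn the arm, and the text does not say that the people doing this work are different from the outcome interviewers.

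If the interviewers were unblinded and also read the scales aloud, their manner or prompting could shift answers on the PSQI and the other self-report scales. Putting the form last would protect the current visit, but an interviewer who gave it at post-intervention would return at follow-up already knowing the arm. Because the pilot is meant to test procedures for a full-scale trial, a loose procedure could carry forward.

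**Working it through.** No published figure is involved. The check has three steps: place the form in the schedule, count what could be exposed, and ask under which arrangements exposure occurs.

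**1. Schedule.** The visit columns of Table 1 run in this order: baseline, actigraphy, during intervention, post-intervention, actigraphy, follow-up, actigraphy. Part 2 is marked in the fourth and sixth columns. Randomisation follows completion of the baseline assessments, so Part 2 is due at 2 of the 3 interviews, and these are both of the post-randomisation ones. Baseline is not at issue.

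**2. Upper limit of exposure.** Scales in Table 1 due at both post-intervention and follow-up, with item counts:

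PSQI 18 + ASHS 33 + PSS-14 14 + PROMIS stress 8 + PROMIS anxiety 8 + PROMIS sleep 8 + MAAS-A 14 = 103 items in 7 scales.

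Hypothesis 2 in section 1 names three primary-outcome instruments: actigraphy, the sleep diary and the PSQI. Actigraphy is recorded by a device. The diary is "electronically accessed using any electronic device via Qualtrics" by the participant. That leaves 1 of 3, the PSQI, with 18 items. The other 103 − 18 = 85 items belong to scales that are not primary-outcome instruments.

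**3. Arrangements consistent or inconsistent with the protocol.**

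| Arrangement | Scales exposed to an unblinded interviewer | Fits the blinding statement? |
|---|---|---|
| Scales self-completed | 0 | Yes, if the interviewers do not handle Part 2 |
| Scales read by interviewer; Part 2 self-completed unseen or given by other staff | 0 | Yes |
| Scales read first, same interviewer then gives Part 2; a different interviewer at follow-up | 0 | Yes, while the scales are collected |
| As above, but the same interviewer returns at follow-up | 7, at follow-up | No |
| Interviewer gives Part 2 before reading the scales | 7, at both visits | No |

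The two arrangements that expose anything both break the protocol's own statement that interviewers are blinded. The others are open to staff who follow it.

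**Evidence on mode.** Table 1 notes that the General Sleep Inventory sits in a baseline survey. The Compensation paragraph in section 3 separates payment for survey data from payment for actigraphy data. Section 10 lists distress while filling in surveys in the randomised pilot among the risks. Section 9 names REDCap, alongside Zoom, as a data-collection platform. Against these, the Data Collection paragraph speaks of interviews and mentions online surveys for absent students. Mode is therefore not settled, but self-completion is plausible as the ordinary route.

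**Other routes to unblinding.** Part 1 is not limited to one arm, so receiving it reveals nothing by itself, although answers could. The feedback interviews are described as process evaluation, in a sentence that does not assign them to the blinded interviewers. Recordings are confined to the facilitator and one staff member, and nothing says that this person also collects outcomes.

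**The case for a change.** The best case for a change is that blinding is claimed without qualification while the schedule contains a form able to defeat it. The safeguard belongs beside the claim. Writing down the form order and sending Part 2 as an electronic link would cost little, because Qualtrics and REDCap are already in use. A pilot whose primary goal is design feasibility is a natural place to settle such a procedure.

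Part of this stands. The text is silent on administrator, mode and order, and one sentence on these would make the protocol easier to audit. But a missing sentence about who hands out a form does not make the results unsound when the governing rule, blinded interviewers, is stated. The attached inventory may already supply the sentence. A stricter rule, keeping those who review recordings or hold feedback interviews away from later outcome collection, assumes enough staff to divide the work. The documents give no number of Phase 2 assessors, so a claim that this needs no extra staff cannot be checked.

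The gain is also limited. The seven scales are self-reports by adolescents who attend arm-specific sessions for seven weeks. Their own expectations can colour their answers whatever the interviewer knows. The measures that do not depend on an interviewer are already in the design.

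**Conclusion.** No change to the plan follows. The observation is accurate: interviewers are declared blinded, a treatment-only form falls at both post-randomisation assessments, and the text does not say how the two are kept apart. It is a gap that study staff can fill sensibly while following the protocol as written.

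Exposure ranges from nothing to 7 scales with 103 items at 2 of 3 assessments, with the PSQI the only primary-outcome instrument among them. The upper end requires that the scales are read aloud, that the same interviewers handle Part 2, and that they do so before the scales at both visits. If Part 2 always comes last, exposure is confined to follow-up and needs the same interviewer to return. The documents establish none of these conditions. The size of any resulting bias cannot be derived from them, and none is claimed. Actigraphy and the diary are unaffected throughout.

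This conclusion assumes that the blinding statement is honoured in practice. Evidence that the outcome interviewers do hand out Part 2 before the scales, or return after doing so, would reopen the question.
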